4.2 Analysis Populations

Population	Description
Enrolled Set	All patients who sign informed consent
Efficacy Analysis Set	All randomized patients who take at least 1 dose of double-blind study treatment. Patients will be included in the treatment group to which they were randomized.
Safety Analysis Set	All randomized patients who take at least 1 dose of double-blind study treatment. Patients will be analyzed according to the treatment they actually received.

If any of the above population definitions result in the same set of patients, then analyses will not be replicated for each population.

4.3 Handling of Dropouts or Missing Data

4.3.1 NIAID Ordinal Scale

Missing values for NIAID ordinal scale during Days 1-28 will be imputed as the worse of the two values recorded before and after the missing value(s), including values after Day 28. If the patient has been discharged, then the imputed value will be, at worst, “7- Not hospitalized, limitation on activities and/or requiring home oxygen.” If there is no recorded value after the missing value, then the missing value will not be imputed.

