Abbreviations: ECG = electrocardiogram; ECMO = extracorporeal membrane oxygenation; ED = early discontinuation; fT4 = free thyroxine; FU = follow-up; h = hours; ICF = informed consent form; IMV = intermittent mandatory ventilation; NIAID = National Institute of Allergy and Infectious Diseases; PK = pharmacokinetic; S = Screening; SO₂ = oxygen saturation; TSH = thyroid stimulating hormone.

- a Any procedure done as a standard of care 1 calendar day prior to ICF may be used as the screening procedure. Screening and Day 1 may occur on the same day.
- b Patients who are discharged from the hospital will complete the Completion or Hospital Discharge visit procedures
- c Patients who discontinue the study prior to study completion will complete the ED visit procedures.
- d Follow-up phone visit 1 should be conducted at 14 days after completion or hospital discharge or early discontinuation, or 28 days after the first dose of study drug, whichever occurs later. Follow-up phone visit 2 should be conducted at 60 days after first dose of study drug.
- e Ensure the onset of illness symptoms are captured, examples include fever, coughing, extreme fatigue, headache, myalgia.
- f Includes respiration rate, heart rate, temperature, and blood pressure. Vital signs need to be recorded once at approximately the same time each day. Post dose vital signs on Days 1 and 15 should be collected at the end of infusion and at approximately 1 hr after end of infusion.
- g If procedures were performed within 1 calendar day prior to infusion as part of standard of care and prior to ICF, that may be used as the sample collection on Day 1.
- h Data should be collected from local COVID19 panel laboratory pre-dose within 1 calendar day ≤Day 1, between 24 and 48 hr postdose on Day 2, and Day 16; and at any time on Days 7, 21, and 28 (or discharge or ED). Collection on Days 16 and 21 to be performed only if a Day 15 dose of study treatment was administered ([Appendix 2](#)).

- i Viral testing is only performed for patients who have undetermined or negative COVID-19 test(s). Viral testing is per the institution's testing guidelines.
- j For pregnancy test, only for women of child-bearing potential.
- k Single 12-lead ECGs will be obtained in the supine position at all indicated timepoints. On Days 1 and 15, ECGs will be collected pre-dose and at the end of infusion.

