Patients who are discharged from the hospital will complete study procedures for a Completion or Hospital Discharge visit (see Section 2). Those patients will not return to the site for evaluation, study procedures, or additional study drug administration. However, patients will be contacted for vital status, including the NIAID ordinal assessment; first phone visit at 14 days after completion or hospital discharge or early discontinuation, or 28 days after the first dose of study drug, whichever occurs later; second phone visit at 60 days after the first dose of study drug. This strategy was chosen to remove the burden of return visits for the hospital and clinical trial staff reflecting limited medical resources in the COVID-19 pandemic and to minimize exposure risk to patients and their caregivers.

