4.12.3.2 NIAID Ordinal Assessment

The NIAID will be assessed daily and defined as the lowest score achieved for that day.

The scoring is based on the clinical status of the patient as described below.

NIAID Score	Description
1	Death

2	Hospitalized, on invasive mechanical ventilation or extracorporeal membrane oxygenation (ECMO)
3	Hospitalized, on non-invasive ventilation or high flow oxygen devices
4	Hospitalized, requiring supplemental oxygen
5	Hospitalized, not requiring supplemental oxygen - requiring ongoing medical care (COVID-19 related or otherwise)
6	Hospitalized, not requiring supplemental oxygen - no longer requires ongoing medical care
7	Not hospitalized, limitation on activities and/or requiring home oxygen
8	Not hospitalized, no limitations on activities

The lowest value from Day 1 through Day 28 for a patient on the NIAID ordinal scale will be analyzed using the van Elteren test adjusting for the randomization stratification factors. The number need to treat (NNT) to prevent one patient from progressing to level 2 or 1 will be calculated. Mean values will be calculated and differences in treatment effect estimates at Days 7, 14 and 28 will be analyzed. Mean value by treatment group will be plotted over time.

[figure not shown]
Time to the first 2-point improvement on the NIAID scale will be analyzed between treatment groups. The time for subjects who did not achieve 2-point improvement will be censored at day 28 and stratification will be ignored in this analysis. A Kaplan-Meier plot with log-rank test will be used to compare treatment groups.

The stacked bar plot(s) representing the proportion of subjects in each score by treatment arm over time will be generated with stratification ignored. An example of such plot is as follows. The details of the score will be included in the footnote of the plot.

In addition to the stacked bar plot based on the original NIAID scores, another stacked bar plot that lumps NIAID scores into four categories will be generated. The four new categories are:

- a. Death (NIAID score = 1),
- b. IMV/ECMO (NIAID score = 2),
- c. Requiring O₂ or medical care (NIAID scores = 3, 4, 5), and
- d. Not requiring O₂ nor medical care (NIAID scores = 6, 7, 8).

Figure 2.0 Example of a Stacked Bar Plot:

4.12.3.3 28-day Mortality

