Mortality will be defined as 28-day all-cause mortality, defined as 672 hours from the time of randomization. All patients will be classified as either “alive at Study Day 28” or, if dead, “dead at Study Day 28.” Patients whose mortality status cannot be determined will be classified as “dead at Study Day 28.” The difference between treatment groups will be analyzed.

The 60-day mortality will be analyzed in a similar fashion.

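### SAP 4.3.1 lets a later death fill missing NIAID scores on days when an undischarged patient was still alive

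*SAP*

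**What the plan says.** SAP 4.3.1 sets the rule for missing NIAID scores on Days 1-28. A gap is "imputed as the worse of the two values recorded before and after the missing value(s), including values after Day 28". Two limits follow. For discharged patients, "If the patient has been discharged, then the imputed value will be, at worst", score 7. And "If there is no recorded value after the missing value, then the missing value will not be imputed".

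The scale runs from 1 (death) to 8 (Protocol 9.1.2.1; SAP 4.12.3.2), so a recorded death is always the worse of two neighbours. Scores after Day 28 come from the phone visits. Protocol 5.4 says that "patients will be contacted for vital status, including the NIAID ordinal assessment". Footnote d to the Schedule of Activities (Protocol Section 2) puts the first call 14 days after completion, discharge or early discontinuation, or 28 days after the first dose, whichever is later. It adds: "Follow-up phone visit 2 should be conducted at 60 days after first dose of study drug".

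The daily scores feed SAP 4.12.3.2: "The lowest value from Day 1 through Day 28 for a patient on the NIAID ordinal scale will be analyzed using the van Elteren test". The same section plans a number needed to treat (NNT) to prevent progression to level 2 or 1, comparisons at Days 7, 14 and 28, mean plots and stacked bars. Death by Day 28 is also defined separately. SAP 4.12.3.3 states: "Mortality will be defined as 28-day all-cause mortality, defined as 672 hours from the time of randomization". SAP 4.12.1 gives the primary endpoint the value -1 only if the patient does not survive through Day 28.

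**The concern.** Taking the worse neighbour is a sensible cautious rule for scores 2 to 8, where the true state on a missing day is uncertain. Death is different: its date is known, and the patient was certainly not in that state the day before. SAP 4.3.1 does not refer to the date of death, and it expressly admits values from after the Day 1-28 window.

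The limit of 7 removes the problem after discharge, which is where the planned gaps lie because daily visits stop. It does not cover three situations: an in-hospital gap before death, a missing Day 28 score in a patient still in hospital, and early discontinuation from the study while in hospital.

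At stake is agreement between secondary endpoints. One patient could be alive at Day 28 in the mortality table and dead at Day 28 in the NIAID tables of the same report, and a Day 1-28 endpoint could count deaths that fell outside its window.

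**Working it through.** The plan gives no figure to reproduce here, so the check applies the rule to hypothetical records.

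**Rule as written.** Imputed score = min(last score before the gap, first score after it); raised to 7 if the day is after discharge; left missing if no later score exists.

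| Patient | Record | Rule gives | True state |
|---|---|---|---|
| 1 | In hospital, score 4 to Day 10, Days 11-13 missing, dies Day 14 | min(4, 1) = 1 on Days 11-13 | Alive on those 3 days |
| 2 | Leaves study Day 5 in hospital at score 4, dies Day 20, recorded at the call around Day 28 | 1 from Day 6 | Alive Days 6-19 (14 days, including Days 7 and 14); score 1 is right from Day 20 |
| 3 | In hospital, score 3 to Day 27, Day 28 missing, dies Day 35, score 1 at the Day 42 call | Day 28 = min(3, 1) = 1; worst score = 1 | Alive at Day 28; worst score 3 |
| 4 | Leaves study Day 10 in hospital at score 4, first call missed, dies Day 40, next record is score 1 on Day 42 | Days 11-28 = 1 (18 days); worst score = 1 | Alive throughout; worst recorded score 4 |
| 5 | Discharged Day 10 at score 7, dies Day 40, first call missed, score 1 at Day 60 | min(7, 1) = 1, raised to 7 | No error |
| 6 | Discharged Day 18 at score 8, dies Day 24, score 1 first recorded Day 32 | min(8, 1) = 1, raised to 7 | Dead on Days 24-28 (5 days) but scored 7 |

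**Reading the table.**
- Patients 1 and 2 died by Day 28, so their worst Day 1-28 score is 1 under any rule. Only day-specific means, comparisons and plots are wrong.
- Patients 3 and 4 died after Day 28. Their Day 28 score and worst score are both wrong, and they conflict with SAP 4.12.3.3 and 4.12.1.
- For the NNT, patients 3 and 4 are newly counted as reaching level 2 or 1. A patient who had already reached score 2 would move from 2 to 1 on the worst score, and the NNT would not change.
- Patient 5 shows the limit working. Patient 6 shows it erring the other way, because it also overrides a death that has already happened.

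**Size per affected patient**, with the planned 100 per arm (SAP 3.2):
- Day 28 death category: 1/100 = 1 percentage point.
- Day 28 mean: (1 - 3)/100 = -0.02 if the true score is 3; (1 - 4)/100 = -0.03 if it is 4.
- Five such patients in one arm, purely as an illustration: 5 points, and -0.10 to -0.15 on the mean.

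**The case against.** **Gaps should be rare where the rule bites.** Scoring in hospital is daily, stopping study drug alone does not end follow-up (Protocol 8.1), and a gap with no later value is not filled. This stands, and it limits the size of the problem. It does not make the rule correct when a gap occurs.

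**Patient 3 may not arise from a Day 27 visit.** The completion visit is the Day 28 visit with a window of one day either side, so a Day 27 score may simply be taken as the Day 28 record. The SAP has no mapping rule either way. The error needs only that Day 28 is missing, for whatever reason. Patient 4 needs a missed first call; patients 1 and 2 need neither condition.

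**The rule may be meant as conservative.** SAP 4.4 gives patients who die the worst outcome. But it does not move the date of death, and NIAID already contains death as a level. Nor is back-dating reliably conservative between arms: if one arm delays death past Day 28, the rule removes that difference for the patients affected.

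**A reader might infer that all later deaths are back-dated.** The documents do not support this, because the limit of 7 blocks it for discharged patients.

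**A reader might also infer a sizeable count of false Day 28 deaths.** Suppose 20-30 patients are in hospital at Day 28, 10-20% of them die on Days 29-60, and one third of completion visits fall on Day 27 and leave Day 28 missing. That gives 20 x 0.10 x 1/3 = 0.7 to 30 x 0.20 x 1/3 = 2 patients. None of these inputs is in the documents. The sum also counts too many deaths: a patient who completes around Day 28 is called at about Day 42, so a death after that call would normally have an alive score before it. With deaths spread evenly over Days 29-60 (a further assumption), 14/32 would qualify, giving 0.3 to 0.9 patients; deaths concentrated early would raise this.

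**Conclusion.** The rule is wrong as written for patients who have not been discharged. It places death on days when they were alive, and where the next recorded value is a death after Day 28 it makes both the Day 28 score and the worst Day 1-28 score equal to 1 for someone alive at Day 28 elsewhere in the analysis.

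The reach is limited. The primary endpoint, 28-day mortality and Complete Response (SAP 4.12.3.1) have their own definitions and are untouched; only NIAID secondary analyses change. SAP 4.16 also lists a worst-NIAID table for the DMC, but does not say whether imputed scores enter it, so no effect there can be asserted.

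The number of patients cannot be derived from the documents and is probably small. The per-patient size rests on 100 per arm and a true Day 28 score of 3 or 4. This should be corrected before the final analysis because the scores contradict known dates of death, not because a large shift in results is expected.

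**What to change.** Add to SAP 4.3.1:

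> Score 1 is assigned on and after the date of death, including after discharge, and is never imputed to an earlier day. For missing days before the date of death, the worse of the neighbouring non-death scores is used (the last recorded non-death score if the only later value is 1), keeping the limit of 7 for days alive after discharge. A death after Day 28 does not enter any Day 1-28 score.

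Applied to the records above, patients 1 and 2 score 4 on their missing days before death, patient 3 has Day 28 and worst score 3, patient 4 has 4 for both, patient 5 is unchanged, and patient 6 scores 1 from Day 24. The worse-of-two rule is kept wherever both neighbours are alive scores; carrying the last score forward for every gap in anyone who later dies would discard it unnecessarily.

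The cost is a few sentences and a small programming change, since the date of death is already needed for the primary and mortality endpoints. The downside is that, in a gap ended by death, the last score alive may be optimistic. A sensitivity analysis using score 2 for in-hospital gaps of this kind would show whether it matters.

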9.1.2. Secondary Efficacy Assessments

9.1.2.1. NIAID Ordinal Assessment

The NIAID will be assessed daily and defined as the lowest score achieved for that day [[NCT04280705](#)].

- 1- Death
- 2- Hospitalized, on invasive mechanical ventilation or extracorporeal membrane oxygenation (ECMO)
- 3- Hospitalized, on non-invasive ventilation or high flow oxygen devices
- 4- Hospitalized, requiring supplemental oxygen
- 5- Hospitalized, not requiring supplemental oxygen - requiring ongoing medical care (COVID-19 related or otherwise)
- 6- Hospitalized, not requiring supplemental oxygen - no longer requires ongoing medical care
- 7- Not hospitalized, limitation on activities and/or requiring home oxygen
- 8- Not hospitalized, no limitations on activities.

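### SAP 4.3.1 sets every imputed NIAID day after discharge to 7 until a phone score exists: 8 cannot occur at Days 7 and 14, the Day 28 7/8 split depends on call and discharge dates, and discharged patients reached at neither call have no post-discharge score

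*SAP*

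**What the plan says.** - **Daily score.** Protocol 9.1.2.1: "The NIAID will be assessed daily and defined as the lowest score achieved for that day". SAP 4.12.3.2 repeats this. Levels 2 to 6 are hospital levels; 7 and 8 are out of hospital.
- **After discharge.** Protocol 5.4: "Those patients will not return to the site for evaluation, study procedures, or additional study drug administration". NIAID is then collected only at two phone visits.
- **Timing of the calls.** Protocol Section 2, footnote d, places phone visit 1 at "14 days after completion or hospital discharge or early discontinuation, or 28 days after the first dose of study drug, whichever occurs later". Phone visit 2 is at Day 60. Both have a window of ±2 days.
- **Imputation.** SAP 4.3.1: a missing score in Days 1-28 "will be imputed as the worse of the two values recorded before and after the missing value(s), including values after Day 28". Then: "If the patient has been discharged, then the imputed value will be, at worst", 7. And: "If there is no recorded value after the missing value, then the missing value will not be imputed".
- **Use.** SAP 4.12.3.2 plots mean scores over time and says "differences in treatment effect estimates at Days 7, 14 and 28 will be analyzed". It also plans an 8-level stacked bar plot and a time to first 2-point improvement, in which patients without the improvement are censored at Day 28.

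**The concern.** The by-day NIAID summaries use an 8-level scale, but for discharged patients the top level is not observed until the first call. Before that, the rule compares a hospital score with a phone score, takes the hospital score as the worse, and raises it to 7. The phone score does not affect the result. Two patients with the same recovery can therefore differ at Day 28 only because one was called a day later or went home a few days later. If the arms differ in discharge timing, the Day 28 contrast will partly reflect that rather than status on Day 28.

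Separately, a patient known to have left hospital alive is at 7 or 8 at that point, yet the rule leaves all later days blank if no phone score follows. In the 2-point analysis, some of these good outcomes then count as no improvement.

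**Working it through.** **1. Timing of phone visit 1.** Call day = the later of (discharge or completion day + 14) and 28 days from first dosing. For a patient completing at Day 28: 28 + 14 = 42, which matches the Day 42 in the Schedule of Activities. The earliest in-window call is 28 − 2 = Day 26. The documents do not settle whether the 28-day target means Study Day 28 or, with dosing on Day 1, Study Day 29. The schedule pairs Day 60 with 60 days from first dose, which favours Day 28. Both were checked.

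**2. The rule as a formula.** For a missing day after discharge: score = max(min(before, after), 7). If nothing is recorded afterwards, the score stays missing. With a discharge-day score of 6 and a call score of 8: max(min(6, 8), 7) = 7.

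**3. Single patients** (6 on the discharge day; 8 at any call that is made):

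| Discharge | Phone visit 1 | Phone visit 2 | Day 14 | Day 28 |
|---|---|---|---|---|
| Day 8 | Day 28 | any | 7 | 8 (recorded) |
| Day 8 | Day 29 | any | 7 | 7 |
| Day 18 | Day 32 | any | in hospital | 7 |
| Day 5 | not reached | Day 60 | 7 | 7 |
| Day 5 | Day 27 | not reached | 7 | missing |
| Day 5 | not reached | not reached | missing | missing |

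**4. All discharge days from 2 to 27, every window offset from −2 to +2, both readings of the target.**
- Days 7 and 14: every patient already discharged scores 7.
- Day 28, discharge by Day 14: 8 if the call falls on Day 28. If it falls on Day 26 or 27, Day 28 is itself imputed and is 8 only if phone visit 2 also records 8. Any call from Day 29 on gives 7.
- Day 28, discharge on Day 15 or 16: 8 only with an early call. The targets are Days 29 and 30, so the call must come at least 1 or 2 days early.
- Day 28, discharge from Day 17: the earliest call is 17 + 14 − 2 = Day 29, so always 7.

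**5. Share of recovered patients (8 at both calls) scored 7 at Day 28.** Let s be the share of them discharged by Day 14. The documents do not give s or the call dates, so both are assumed. Early calls after Day 15-16 discharges are ignored.

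| s | Call exactly Day 28: 1 − s | Even over Days 26-30: 1 − 0.6s | Even over Days 27-31: 1 − 0.4s | Call exactly Day 29 |
|---|---|---|---|---|
| 30% | 70% | 82% | 88% | 100% |
| 50% | 50% | 70% | 80% | 100% |
| 70% | 30% | 58% | 72% | 100% |
| 90% | 10% | 46% | 64% | 100% |

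**6. Two-point improvement.** Baseline 5 needs 7, baseline 4 needs 6, and baseline 3 needs 5. A baseline-5 patient can never qualify in hospital. A baseline-3 or baseline-4 patient needs the discharge level only if the 2 points were not already gained there. Illustration, with assumed figures: if 80% are discharged and 5% of those are reached at neither call, 0.80 × 0.05 = 4% of patients lose their post-discharge score. An improvement rate of 80% could then fall to no lower than 76%. This is an upper bound on the loss, because it supposes that none of them had already improved by 2 points in hospital.

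**The case against.** The reach is limited, and this stands. The van Elteren test of the lowest score over Days 1-28 and the number needed to treat to avoid level 2 or 1 do not change when 7 replaces 8, because the patient already has a lower hospital score. The second stacked bar plot merges 6, 7 and 8. No patient with baseline 3, 4 or 5 needs an 8 for a 2-point improvement. The primary endpoint does not use NIAID. The rule is the same in both blinded arms, so it loses information; no direction of bias has been shown.

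The result also rests on the discharge-day score being a hospital score. The schedule includes NIAID at the discharge visit, and if a site entered 8 there and the calls also gave 8, the imputed days would be 8. The lowest-of-day definition argues against that entry.

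A reader might go further and infer that most recovered patients score 7 at Day 28. The documents give neither discharge nor call dates, and the table shows shares well below and well above half. A reader might also infer that any patient missed at phone visit 1 has no score. That is too broad: a Day 60 score alone yields 7 on the post-discharge days, and in-hospital scores remain in every case.

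Finally, carrying 7 to Day 28 for every discharged patient would conflict with SAP 4.12.3.3, which counts unknown mortality status as dead, and with SAP 4.3.2, which makes unknown survival a non-response. The fix has to respect that.

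**Conclusion.** The point holds in a limited form and should be corrected. Given the lowest-of-day definition, score 8 is impossible at Days 7 and 14. At Day 28 the split between 7 and 8 depends partly on call and discharge dates: discharge from Day 17 on always gives 7, and for discharge by Day 14 a one-day shift of the call can change the score. How many patients this touches is not determinable from the documents; about 10% to 100% of recovered patients is the range under the assumed dates.

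Discharged patients reached at neither call have no post-discharge score. Those who still need the discharge level to qualify are censored at Day 28 as not improved. That always applies to baseline 5, and to baseline 3 or 4 only without an earlier 2-point gain in hospital.

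The analyses affected are the Day 7, 14 and 28 means and differences, the mean plot, the 8-level bars and, for unreached patients, the time to 2-point improvement.

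**What to change.** Change SAP 4.3.1 and 4.12.3.2:

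1. In the Day 7, 14 and 28 means, the treatment differences and the 8-level plots, combine 7 and 8 into one not-hospitalized level. Compare 7 with 8 at phone visits 1 and 2, where the distinction is observed.
2. Count live discharge as reaching at least 7 from the day after discharge, whether or not a phone score follows. Where this qualifies, it is the event date for the 2-point improvement.
3. Carry that level to Day 28 only for patients known to be alive, from phone contact or the vital status search in Protocol 8.3, and not known to be readmitted. Treat patients of unknown vital status consistently with SAP 4.12.3.3 and 4.3.2.

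The cost is SAP wording only; discharge and hospitalization data are already collected. Staff who are still blinded should settle it before final unblinding. The downside is that the 7 versus 8 distinction, including Day 28 scores of 8 that were actually recorded, moves out of the Day 28 summaries into a phone-visit table.

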4.4 Handling of Deaths in Efficacy Analyses

For the endpoint that does not contain mortality as a component, such as length of hospital stay during Days 1 to 28, they will be assumed in the hospital for 29 days. The median length in such case will be more appropriated to be reported.

Other efficacy endpoints will handle death via similar imputation: patients who die will be assumed to have experienced the worst outcome. These analyses include percentage of patients discharged from hospital at Day 28, percentage of patients who ever received each of the various types of supportive care, and length of the various types of supportive care.

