4.12 Efficacy Analyses

4.12.1 Primary Outcome and Methodology

The primary outcome variable will be defined as follows:

- For patients who survive through day 28, the value is the number of days free of mechanical ventilation.
- For patients who do not survive through day 28, the value is set to -1.

If a patient is discharged from the hospital before day 28, and if the patient is still alive at day 28, then days between hospital discharge and Day 28 will be considered ventilator free. A table listing the counts of patients with each number of ventilator free days, including patients with -1 values due to death, will be presented by treatment group. The statistical method for this endpoint will be based on the Wilcoxon rank-sum test using the van Elteren test adjusting for the randomization stratification factors (age group, sex, and site).

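### After discharge, SAP 4.3.1 limits imputed NIAID scores to 7 even over a known death or readmission, and SAP 4.12.1 credits ventilated readmission days as ventilator free

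*SAP*

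**What the plan says.** **NIAID missing data (SAP 4.3.1).** The general rule is "Missing values for NIAID ordinal scale during Days 1-28 will be imputed as the worse of the two values recorded before and after" the gap, and scores recorded after Day 28 may serve as the later value. For discharged patients there is a limit: "If the patient has been discharged, then the imputed value will be, at worst", score 7. The last sentence reads: "If there is no recorded value after the missing value, then the missing value will not be imputed".

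**Where post-discharge scores come from.** Under Protocol 5.4 and Table 2-1 (note d), discharged patients do not return to the site. Their next NIAID score is taken by phone at the later of 14 days after discharge and 28 days after the first dose, and then at Day 60.

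**Deaths (SAP 4.4).** After a rule for length of stay, it says "Other efficacy endpoints will handle death via similar imputation", meaning that "patients who die will be assumed to have experienced the worst outcome". The examples begin "These analyses include percentage of patients discharged from hospital at Day 28" and go on to supportive care. NIAID is not named, and 4.3.1 and 4.4 do not refer to each other.

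**NIAID analyses (SAP 4.12.3.2).** These are a van Elteren test on each patient's lowest score over Days 1 to 28, a number needed to treat (NNT) to prevent progression to 2 or 1, comparisons of means at Days 7, 14 and 28, and stacked bars with Death as a category. Also, "Mean value by treatment group will be plotted over time".

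**Ventilator free days.** For a patient discharged early and alive at Day 28, SAP 4.12.1 says "then days between hospital discharge and Day 28 will be considered ventilator free". Protocol 10.3.3.1 gives the same credit. Protocol 9.1.1 counts only days on which no ventilator is required.

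**The concern.** Both rules are triggered by the discharge itself and not by where the patient is on the day being scored. Once a patient has gone home, nothing in either rule ends the favourable assumption when a death or a return to hospital becomes known. Daily scoring stops at discharge, so for early discharges most of the remaining days to Day 28 are imputed and the limit is in routine use.

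At stake are the by-day NIAID means and plots, and, for events after discharge, possibly the lowest-score test and the NNT. The ventilator-free-day credit touches the primary endpoint. A further question is whether a patient who dies in hospital keeps score 1 on later days or drops out of the daily summaries.

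**Working it through.** The documents give no expected NIAID mean, so there is no stated figure to reproduce.

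**Step 1. Apply SAP 4.3.1 as written to single patients.**

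| Situation | Score before gap | Next recorded score | Missing days become |
|---|---|---|---|
| Still in hospital | 4 | 2 | 2 |
| Discharged | 8 | 8 | 8 |
| Discharged | 7 | 4 | 7 |
| Discharged | 7 | 2 | 7 |
| Discharged | 7 | 1 (death) | 7 |
| Discharged, no later contact | 8 | none | left missing |
| Died in hospital, nothing entered later | 1 | none | left missing |

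The limit affects imputed values only. Recorded scores, including phone scores, stand.

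**Step 2. Death after discharge.** Take discharge on Day 20 and death on Day 25.

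- The phone visit falls at the later of Day 20 + 14 = Day 34 and about Day 28, so around Day 34. It records score 1.
- The worse neighbour for Day 28 is 1, but the limit raises it to 7. The error is 7 - 1 = 6 points, or 6/100 = 0.06 on the mean of a 100-patient arm.
- For a patient readmitted and ventilated on Day 28, the error is 7 - 2 = 5 points, or 0.05 on the arm mean.
- The phone score lies outside Days 1 to 28. Unless a score is entered for the date of death, the lowest-score test and the NNT see only the in-hospital scores and the imputed 7s. The patient then counts as not having progressed to 1.
- The same patient is dead in 28-day mortality (SAP 4.12.3.3) and scores -1 on the primary endpoint.

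**Step 3. Ventilator free days.** Take a patient not ventilated in the first stay, discharged, readmitted and ventilated for k days before Day 28, and alive at Day 28. Protocol 9.1.1 gives 28 - k. SAP 4.12.1 gives 28, a tie with patients who were never ventilated. The documents give neither the frequency of readmission nor k.

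**Step 4. Death in hospital, if 4.3.1 were applied without 4.4.** SAP 3.2 plans 12.5% mortality on placebo and a 50% improvement, so 12.5% x 0.5 = 6.25% on LY3127804. Let m be the mean Day 28 score of survivors, assumed equal in both arms.

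- Death scored 1: [(1 - 0.0625)m + 0.0625] - [(1 - 0.125)m + 0.125] = 0.0625(m - 1).
- m = 7.0: 6.625 - 6.250 = 0.375. m = 7.5: 0.0625 x 6.5 = 0.406.
- Wider range: m = 5 gives 0.25, and m = 8 gives 0.44.
- Day 14, assuming half the deaths have occurred by then: 0.03125 x 6 = 0.19 at m = 7.
- Deaths dropped: m - m = 0 at either day.

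SAP 4.1 computes percentages on non-missing observations, so on this reading the dead would also leave the denominators of the stacked bars.

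**The case against.** The strongest reply concerns death in hospital. SAP 4.4 is the section on deaths, its list of examples is open, and the worst NIAID outcome is 1. A dead patient's status is known, so the sentence on having no later value fits loss to follow-up better. Stacked bars over time with Death as a category make little sense if deaths vanish the next day. This largely stands. A reader might infer that the plan removes the dead from the NIAID means, but the documents support that only as one reading.

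A reader might also infer that the arm with more deaths would look better. Step 4 does not show that: it gives a difference of 0, which is a loss of effect and not a reversal. A reversal needs a further assumption. Suppose the 6.25% of patients saved are all still at score 2 on Day 28 and the others average 7. Dropping deaths then gives (0.875 x 7 + 0.0625 x 2)/0.9375 - 7 = -0.33. Scoring them 1 gives 6.3125 - 6.25 = +0.06. Nothing in the documents says that this would be the pattern.

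On the limit of 7, the defence is that it has a purpose: without it, an inpatient score or a late phone score would be spread over days spent at home. That stands, and is a reason to keep the limit for those days. One may also read it as meant only while the patient is out of hospital, or say that 4.4 overrides it for deaths. But the text is triggered by having been discharged, no order of precedence is given, and 4.4 does not deal with readmission.

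It would be too strong to say that deterioration after discharge is erased from every analysis. A 1 or 2 recorded within Days 1 to 28 still counts, and for patients discharged by Day 14 the phone score falls at about Day 28 and may itself be the Day 28 value.

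**Conclusion.** Two rules give wrong values as written. The limit in SAP 4.3.1 can score a patient as at home on days when he or she is known to be dead or back in hospital. The credit in SAP 4.12.1 can count ventilated days as ventilator free, contrary to Protocol 9.1.1. The error is 5 or 6 NIAID points per affected patient-day for the events in Step 2, and one ventilator free day per ventilated readmission day. The total cannot be stated without a rate of readmission or post-discharge death.

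The carry-forward of in-hospital death is an ambiguity. Its possible cost of 0.38 to 0.41 points at Day 28 rests on the planning mortality and on assumed equal survivor means of 7.0 to 7.5. It would be confined to by-day means and plots: the primary endpoint, 28-day mortality and the lowest-score test for recorded in-hospital deaths are unaffected. It still deserves a sentence, because two programmers following the SAP could report different means.

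**What to change.** - **SAP 4.3.1:** assign score 1 from the date of death through Day 28, in or out of hospital, and refer to 4.4.
- **SAP 4.3.1:** apply the limit of 7 only to days before a documented readmission or death. For later days, use the recorded score or, if it is missing, the worse neighbouring value.
- **SAP 4.12.1:** credit post-discharge days as ventilator free except days of documented readmission with mechanical ventilation. Note that this aligns the credit, also given in Protocol 10.3.3.1, with the definition in Protocol 9.1.1.

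The cost is a few sentences and some derivation code. The inputs are death dates, the hospitalization and supportive-care data already listed in SAP 5.2, and the dates of starting and stopping IMV/ECMO that Table 2-1 (note p) asks sites to capture with the NIAID assessment. SAP 4.16.1 describes the futility analysis, which used ventilator free days, in the past tense. The sponsor should therefore record when the change to 4.12.1 is made relative to unblinding.
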